7 STUDY PROCEDURES AND ASSESSMENTS

Refer to the Alternate Schedule of Assessments in [Section [12.11](#) Clinical Study Continuity] for acceptable alternate methods to assess safety and efficacy parameters in the event the study is interrupted due to a crisis (e.g., natural disaster, pandemic).

7.1 Efficacy Assessments

7.1.1 Imaging picture of tympanic membrane by endoscope

At Screening, an imaging picture of the tympanic membrane for both ears will be captured by endoscope. After the treated ear is determined at Day 1, an imaging picture will be taken only of the treated ear throughout the study.

An imaging picture of the tympanic membrane will be recorded to support evaluation of efficacy endpoints at all visits. TMP closure is defined as TMP closure without presence of pin hole. All images from each visit will be sent to a central imaging vendor for measurement and interpretation. TMP size calculation and evaluation of complete closure will be performed by central imaging vendor and detailed instruction will be described in Independent Review Charter. See the SAD and Single Dose Expansion Schedule of Assessments ([Table 2](#) and [Table 3](#)) and MAD and Multiple Dose Expansion Schedule of Assessments ([Table 4](#) and [Table 5](#)) for timing of procedures.

7.1.2 Microscopic Ear Examination

The site investigator will examine the tympanic membrane by microscope. TMP closure will be evaluated at all visits except for Screening and Day 1, and will be recorded in the eCRF.

7.1.3 Pure Tone Audiometry

Pure Tone Audiometry (PTA) is a behavioral test and generally the first quantitative hearing test done to assess the nature and degree of hearing loss in adults and in children. This

measure involves the peripheral and central auditory systems. Pure tone air conduction and bone conduction tests determine whether or not there is any hearing loss; what type of hearing loss it is (conductive, sensorineural or mixed hearing loss); the frequencies that are affected (configuration); magnitude of hearing loss (intensity) and whether hearing loss is unilateral or bilateral. The result is plotted on an audiogram, which is a graph displaying intensity as a function of frequency.

PTA will be performed on the bilateral ears at Screening and will be tested only for the treated ear after the treatment side is determined by investigator at Day 1. This will be performed on a calibrated audiometer by a licensed audiologist.

For the efficacy evaluation, PTA will be measured following different frequencies:

Air: 250 Hz, 500 Hz, 1 kHz, 2 kHz, 4 kHz, and 8 kHz

Bone: 500 Hz, 1 kHz, 2 kHz, and 4 kHz

Follow the Schedule of Assessments ([Table 2](#), [Table 3](#), [Table 4](#) and [Table 5](#)) for timing of procedures.

PTA result(s) (decibel at each frequency) will be recorded in the eCRF at each visit.

7.1.4 Tympanometry

Tympanometry (an objective test of middle-ear function) is an examination used to test the condition of the middle ear and mobility of the tympanic membrane (TM) by creating variations of air pressure in the ear canal. Tympanometry will be performed on the bilateral ear at Screening and only for the treated ear for the remaining study visits.

Tympanogram type (A, Ad, As, B or C) and ear canal volume (ECV) will be recorded in the eCRF. Tympanometry will be performed at Screening, Day 1 and Day 57 (SAD) or Day 85 (single dose expansion and MAD) or Day 113 (multiple dose expansion) or EOS Visits. The assessment will be performed by a licensed audiologist on a calibrated tympanometer. A print-out containing the tympanogram will be collected from the machine or, if no print out is available, the tympanogram should be drawn and stored in the source documents.

7.2 Safety Assessments

Single Dose study procedures and their timing are summarized in the Schedule of Assessments ([Table 2](#) and [Table 3](#)). Multiple Dose study procedures and their timing are summarized in the Schedule of Assessments ([Table 4](#) and [Table 5](#)). Protocol waivers or exemptions are not allowed.

Procedures conducted as part of a subject's routine clinical management (i.e., standard of care) obtained before signing the ICF may be utilized for screening or baseline purposes, provided the procedures met the protocol-specified criteria and were performed within the time frame, as defined in the Single Dose Schedule of Assessments ([Table 2](#) and [Table 3](#)) and the Multiple Dose Schedule of Assessments ([Table 4](#) and [Table 5](#)).

7.2.1 Adverse Events

See [Section 7.3 Adverse Events and Other Safety Aspects] for information regarding AE collection and data handling.

7.2.2 Laboratory Assessments

- Will be performed at Screening for eligibility purposes.
- The investigator or sub-investigator must review the laboratory report and document this review.
- Clinical significance of out-of-range laboratory findings is to be determined and documented by the investigator or sub-investigator who is a qualified physician.
- Unscheduled laboratory assessments may be performed for Adverse Events.

7.2.3 Vital Signs

Vital signs will include systolic and diastolic blood pressure (mmHg), heart rate (bpm), and body temperature (°F / °C). Vital signs will be performed according to the Schedule of Assessments ([Table 2](#), [Table 3](#), [Table 4](#), [Table 5](#)). Additional vital sign assessments may be taken as indicated or according to institutional standard procedure.

7.2.4 Physical Examination

A physical examination of the subject will be conducted by a medically qualified person at the Screening Visit. This will consist of an examination of general appearance, nose, throat, neck, and lymph nodes, as well as measurements of height and weight. A symptom-directed physical may be performed at any of the other visits, if necessary.

The screening physical examination also includes any significant, ongoing medical conditions.

7.2.5 Microscopic Ear Examination

At Screening, both ears will be examined microscopically to identify the TMP and evaluate the eligibility of the subject for the study. Only the ASP0598 Otic Solution or placebo treated ear will be examined at Day 1 and at subsequent visits.

Local skin reaction around the application site will be examined at 60 minutes after the treatment at Day 1 for single dose and Days 1, 15, and 29 for multiple dose and throughout the observation period. Skin toxicity will be evaluated by the Modified Brighton Grading Scheme ([Appendix 12.9](#)) and recorded in the eCRF.

7.2.6 Pure Tone Audiometry for Ototoxicity Assessment

For the ototoxicity evaluation, bone conduction hearing level at 1, 2 and 4 kHz will be measured by PTA. PTA for ototoxicity assessment will be performed for the treated ear on a calibrated audiometer by a licensed audiologist.

Bone Conduction hearing level measured by PTA will be performed according to the Schedule of Assessments ([Table 2](#), [Table 3](#), [Table 4](#), [Table 5](#)).

PTA result (decibel at each frequency) will be recorded in the eCRF at each visit.

7.2.7 Tinnitus Visual Analog Scale

Subjects will be given the Tinnitus Visual Analog Scale (Appendix 12.10) to rate their tinnitus at all visits. The Scale is a numeric scale and ranges from 0 (not at all strong or loud) to 10 (extremely strong or loud). The subject's response will be recorded in the eCRF at each visit. The scale is designed to assess the loudness of the subject's tinnitus, its annoyance, the degree of stress it was causing to the subject, and how well the subject was coping with the tinnitus.

7.2.8 Order of Assessments

Refer to and Figures 4 and 5 (Single Dose) and Figures 6 and 7 (Multiple Dose): Otology Examination Flow Chart for the order of assessments.

7.3 Adverse Events and Other Safety Aspects

The definitions of an AE or SAE can be found in [Appendix 12.4 Adverse Events: Definitions and Procedures for Recording, Evaluating, Follow-up or Reporting].

The investigator and medically qualified designee(s) are responsible for detecting, documenting and recording events that met the definition of an AE or SAE.

7.3.1 Time Period for Collecting Adverse Event and Serious Adverse Event Information

In order to identify any events that may be associated with study procedures and could lead to a change in the conduct of the study, Astellas collects AEs even if the subject has not received IP. AE collection begins after the signing of the ICF and will be collected until 14 days after the last study visit or when the subject is determined to be a screen failure.

7.3.2 Method of Detecting Adverse Events and Serious Adverse Events

The methods of recording, evaluating and assessing seriousness, causality and severity of AEs and SAEs are described in [Appendix 12.4 Adverse Events: Definitions and Procedures for Recording, Evaluating, Follow-up or Reporting]. Care will be taken not to introduce bias when detecting AEs and/or SAEs. Open-ended and nonleading verbal questioning of the subject is the preferred method to inquire about AE occurrences.

An AE with a change in severity is recorded as a new AE.

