9.5.1 Adverse Events

AEs will be coded using MedDRA.

A TEAE is defined as an AE observed after starting administration of the study drug through EOS visit. A drug-related TEAE is defined as any TEAE with a causal relationship assessed as “yes” by the investigator.

An overview of TEAEs and Death by treatment group will be presented. In addition, the following summaries will be presented by SOC and PT:

- TEAEs by treatment group
- Drug-related TEAEs by treatment group
- Serious TEAEs by treatment group
- Drug-related serious TEAEs by treatment group

An overview of TEAEs of special interest by treatment group will be presented. The following summaries will be presented by SOC and PT:

- TEAEs of special interest by treatment group
- Serious TEAEs of special interest by treatment group

Details about selection of AEs of special interest will be provided in the SAP.

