5 EFFICACY AND SAFETY ENDPOINTS

5.1 Primary Safety Endpoint(s)

- Treatment-emergent adverse events (TEAEs)
 - **TEAE:** an AE observed after starting administration of the study drug through end of study visit. If an AE occurs on Day 1 and the onset check box is marked “Onset after the dose of study drug” or the onset check box is left blank, then the AE will be considered TEAE. Refer to Section [6.9.1](#) for end day of end of study visit definition.
 - **Drug-related TEAE:** any TEAE with a causal relationship assessed as “yes” by the investigator. If the relationship is missing then it is considered as drug-related.

Imputed date for AE onset date may be used to determine TEAE (Section [6.9.3.1](#)).

The investigator will use the following definitions to rate the severity of each AE:

- Mild
- Moderate
- Severe

- Incidence of AEs of special interest will be defined as shown below.
 1. Cholesteatoma or neoplasm
 2. Ototoxic symptoms (tinnitus, sensorineural hearing loss, dizziness)
 3. Otitis media or otitis externa

AEs of special interest will be identified using custom MedDRA queries (CMQs). Detailed information about AEs of special interest is provided in Appendices 1, 2 and 3.

- Change from baseline in bone conduction hearing at 1, 2, 4 kHz by Pure Tone Audiometry (PTA)

A lower value indicates better level of hearing.

For the change from baseline, a negative value (decrease from baseline) indicates improvement (i.e., better level of hearing).

Mean bone conduction hearing (dB):

Arithmetic mean of the values at 1, 2 and 4 kHz. If the value is missing for any of the 3 frequencies, then the mean value will be set to missing.

- Change from baseline in Tinnitus Visual Analog Scale (TVAS)

The TVAS is a numeric scale and ranges from 0 (not at all strong or loud) to 10 (extremely strong or loud). A lower value indicates less level of discomfort.

For the change from baseline, a negative value (decrease from baseline) indicates improvement (i.e., less level of discomfort).

TVAS may be reported for one of the following areas: ear (left, right or bilateral) or other.

At a time point, if a subject did not experience tinnitus, TVAS will be reported as 0. In this case, the TVAS will be considered as 0 for all two areas.

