6.5.1 Adverse Events

AEs will be coded using MedDRA.

For the AEs, the following summaries will be presented:

- An overview of TEAEs and deaths
 - Number of TEAEs
 - Number and percentage of subjects with TEAEs
 - Number of drug-related TEAEs
 - Number and percentage of subjects with drug-related TEAEs
 - Number of serious TEAEs
 - Number and percentage of subjects with serious TEAEs
 - Number of serious drug-related TEAEs
 - Number and percentage of subjects with serious drug-related TEAEs
 - Number of TEAEs leading to treatment discontinuation (MAD and MDE only)

- Number of deaths
- Number and percentage of subjects with TEAEs by SOC and PT for the following:
 - 1) TEAEs
 - 2) Drug-related TEAEs
 - 3) TEAEs Leading to Treatment Discontinuation (MAD and MDE)
 - 4) Serious TEAEs and including number of events
 - 5) Drug-related serious TEAEs and including number of events
 - 6) Common ($\geq 15\%$ in any treatment group) TEAEs for expansion only
 - 7) TEAEs excluding serious AEs and including number of events and number of threshold events. Here threshold equals 5%. This summary will be created only if at least one serious TEAE is present.
- An overview of TEAEs of interest
 - Number of TEAEs of interest
 - Number and percentage of subjects with TEAEs of interest
 - Number of drug-related TEAEs of interest
 - Number and percentage of subjects with drug-related TEAEs of interest
 - Number of serious TEAEs of interest
 - Number and percentage of subjects with serious TEAEs of interest
 - Number of serious drug-related TEAEs of interest
 - Number and percentage of subjects with serious drug-related TEAEs of interest

The above summary will present results for any TEAEs of interest and each of the TEAEs of interest: Cholesteatoma or neoplasm, Ototoxic symptoms (tinnitus, sensorineural hearing loss, dizziness) and Otitis media or otitis externa.

- Number and percentage of subjects with TEAEs of special interest by SOC and PT for the following:
 - 1) TEAEs of special interest for Cholesteatoma or neoplasm
 - 2) TEAEs of special interest for Ototoxic symptoms (tinnitus, sensorineural hearing loss, dizziness)
 - 3) TEAEs of special interest for Otitis media or otitis externa
 - 4) Serious TEAEs of special interest for Cholesteatoma or neoplasm and including number of events
 - 5) Serious TEAEs of special interest for Ototoxic symptoms (tinnitus, sensorineural hearing loss, dizziness) and including number of events

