6.9 Additional Conventions

6.9.1 Analysis Windows for Safety Variables

For the assessments where the summaries and/or analyses are presented by analysis visit during study period, post baseline values will not contribute to the safety analyses:

- SAD: if the study day of the value is > minimum(study day of end of study visit, 57) + 7 days.
- Single dose expansion and MAD: if the study day of the value is > minimum(study day of end of study visit, 85) + 7 days.
- Multiple dose expansion: if the study day of the value is > minimum (study day of end of study visit, 113) + 7 days.

For the assessments where the summaries and/or analyses are not presented by analysis visit during study period (AEs, previous and concomitant medications and modified brighton grading scheme), end day of end of study visit is defined as follows:

- SAD: minimum(study day of end of study visit, 57) + 7 days.
- Single dose expansion and MAD: minimum(study day of end of study visit, 85) + 7 days.
- Multiple dose expansion: minimum (study day of end of study visit, 113) + 7 days.

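### As written, a screening AE that only improves after dosing counts as a TEAE, because any severity change opens a new record and treatment emergence is defined by timing alone

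*Protocol*

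**What the plan says.** - **Recording.** Protocol 7.3.2: "An AE with a change in severity is recorded as a new AE". No direction of change is given. Appendix 12.4, to which the section refers, adds none.
- **Collection period.** Protocol 7.3.1: "AE collection begins after the signing of the ICF and will be collected until 14 days after the last study visit". Screening runs from Day -28 to Day -1, so AE records can exist before dosing.
- **TEAE definition.** Protocol 9.5.1: "A TEAE is defined as an AE observed after starting administration of the study drug through EOS visit". SAP 5.1 has the same timing rule. Neither requires the event to be new, or worse than before dosing.
- **What decides status.** The onset date of the record: "Imputed date for AE onset date may be used to determine TEAE" (SAP 5.1).
- **End of the window.** SAP 6.9.1 closes it at, for example, "SAD: minimum(study day of end of study visit, 57) + 7 days". The other parts use Day 85 or Day 113 in place of 57.
- **Summaries.** SAP 6.5.1 reports subjects with TEAEs (number and percentage) and also counts of events, including a row headed "Number of TEAEs of interest". It has no rule that links successive records of one episode.
- **Role.** TEAEs and AESI incidence are primary endpoints (Protocol 3.1 and 9.5). Protocol 9.5 plans no hypothesis test on safety.

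**The concern.** Each rule is reasonable alone; the difficulty is the combination. If improvement opens a record, and a record with a post-dose start date is treatment-emergent whatever came before it, then recovery from a screening event is tabulated as something that emerged on treatment. Dizziness and tinnitus are both listed in SAP Appendix 2, so the same record also enters the ototoxicity AESI tables.

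The SAP handles the parallel problem elsewhere. SAP 6.5.4 takes the worst grade when the Modified Brighton grade changes within an interval, and SAP 6.2.2 counts repeat deviations from one criterion once. AEs, which feed the primary endpoint, have neither rule.

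At stake is how far the descriptive safety tables can be trusted in very small groups. The Dose Escalation Committee reviews TEAEs and AESIs for each cohort (Protocol 4.1.1.2), and safety results inform the decision to open the expansion parts (Protocol 9.10).

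**Working it through.** The plan states no figure on this point, so there is none to reproduce. I applied the written rules to three invented severity histories and compared the result with a new-or-worsened rule that counts one event per episode.

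**Step 1. Rules applied.** Each severity change starts a new record (Protocol 7.3.2). A record is a TEAE if it starts after first dose and no later than the end of the window. For SAD that end is at most 57 + 7 = Day 64 (SAP 6.9.1).

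**Step 2. Histories (assumed, not from the documents).**

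| History | TEAE events as written | Subjects with a TEAE as written | Events if new or worsened, one per episode |
|---|---|---|---|
| A: moderate at screening, mild after dosing | 1 | 1 | 0 |
| B: mild at screening; then moderate, severe, moderate, mild after dosing | 4 | 1 | 1 |
| C: starts after dosing; mild, moderate, mild | 3 | 1 | 1 |

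A shows the misclassification: a subject with no new or worse event becomes a subject with a TEAE. B and C show the repeat counting. The event count rises to 4 or 3, but the subject count stays at 1 under either rule. Repeat counting is therefore confined to rows that count events: the two overview tables, the serious-event tables and the conditional table that excludes serious AEs.

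**Step 3. Largest effect of one history-A subject on an incidence row.** The formula is 100/n, with group sizes from Protocol 6.3.6.

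- SAD active group, n = 4: 100/4 = 25 points. The same applies to pooled placebo if all cohorts run: 4 cohorts × 1 = 4 in SAD, 2 cohorts × 2 = 4 in MAD.
- MAD active group, n = 6: 100/6 = 16.7 points.
- Expansion group, n = 13: 100/13 = 7.7 points.

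These are ceilings. If the subject already has another TEAE that qualifies for the same row, the row moves by 0.

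**Step 4. A planned cut-off that one subject can cross.** SAP 6.5.1 tabulates common TEAEs in the expansion parts at 15% or more in any group. With 13 subjects, one case is 1/13 = 7.7% and two are 2/13 = 15.4%. One misclassified subject can therefore lift a preferred term over the line.

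**The case against.** **Improvement is not an AE.** Protocol 12.4.1 defines an AE as something untoward and mentions disease that is new or exacerbated. On that reading, an easing symptom is not an AE and should not be recorded. This is arguable, but the new-or-exacerbated wording qualifies disease, whereas 7.3.2 speaks of any change in severity. It does not override the recording rule. At best the two texts pull apart, which the SAP should settle.

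**The affected pool is small.** Conditions ongoing at consent are medical history (Protocol 10.2.2). Active otorrhea and external-canal inflammation in the study ear are exclusions (Protocol 5.2), rechecked on Day 1. Case A needs an AE that starts after consent, is still present at dosing, later eases, and is entered as a new record. This stands: the documents give no frequency, and it may be low.

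**Little turns on it for decisions.** The escalation stopping rules require relatedness (Protocol 4.1.1.3), drug-related TEAEs are tabulated separately, and no safety hypothesis is tested. This also stands.

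**The recording rule is useful.** Because status follows the onset date, a pre-dose AE that worsens after dosing would keep its pre-dose onset, and could be missed, unless a new record were opened. This is right and is why the rule should remain.

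**The link may be made elsewhere.** eCRF instructions or table specifications might join records. They are not among the documents, and the SAP text states no such rule.

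A reader might also infer that one episode can inflate the whole primary endpoint several times over. The documents do not support that: AESI is an incidence endpoint, and the subject rows count each subject once.

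**Conclusion.** The gap is real and modest. Followed literally, the plan classes a screening AE that only improves after dosing as a TEAE, and as an AESI where its term is listed. One such case moves a subject-incidence row by at most 25, 16.7 or 7.7 points at n = 4, 6 or 13. This assumes full groups and no other qualifying TEAE in that subject. It would be wrong to read these figures as an expected bias, because nothing in the documents gives the rate of such cases.

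Repeat counting of one episode is a separate, narrower effect limited to the event-count rows. Nor does every AE after dosing qualify: the TEAE window ends at the earlier of the EOS day and the nominal day, plus 7 days, although AEs are collected until 14 days after the last visit. The consequence is a possible distortion of descriptive primary safety summaries. No test, error rate or power figure is affected.

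**What to change.** 1. **SAP 5.1, and the key-terms list that repeats the definition.** Within the existing window, define a TEAE as an AE that is new after first dose, or one that continues a pre-dose AE with severity higher than its severity at dosing. A record is a continuation if it has the same preferred term, the same ear where applicable, and starts when the previous record ends. A continuation record of equal or lower severity is not a TEAE.
2. **SAP 6.5.1, event-count rows only.** Count contiguous continuation records of one episode as one event. The contiguity and same-ear conditions matter: joining every record of a preferred term would merge separate episodes, or left- and right-ear events.
3. **Leave as they are.** Keep the recording rule in Protocol 7.3.2, so that post-dose worsening is still captured. Keep every raw record in the listings with its own onset, severity, causality and seriousness.

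The definition in Protocol 9.5.1 should be brought into line, or the difference explained in the study report. The cost is SAP wording and one added derivation step. That step relies on dates to link records, so incomplete or inexact dates will leave some links to judgement. For the escalation parts, Protocol 9 and SAP 1 require SAP changes to be approved before unblinding for the interim analysis.
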